Serum E₂, FSH and LH concentrations and change from baseline will be summarised at each time point, using descriptive statistics (n, mean, median, SD and minimum and maximum values) and the 95% CI for the difference between treatment groups in mean concentration values and mean change from baseline values will be presented for each parameter.

The 95% CI for the difference in mean and change from baseline values are calculated using a linear model for repeated measurements adjusting for baseline value and its interaction with visit, treatment group and its interaction with visit, and randomisation stratification factors (endometriotic surgical history and the severity of endometriosis-associated pelvic pain at baseline) and its interaction with treatment group. In a case where the stratification factor recorded in the eCRF and IWRS are inconsistent, the eCRF data will be retained. Baseline and its interaction with visit will be added in the above SAS code.

Time to Menses Recovery:

Time to menses recovery will be defined as the time (in days) between date of last dose of study drug and date of first day the subject observed menstrual bleeding of the next menstrual period. Any subjects withdrawing from the study without menstrual bleeding will be censored in the analysis at the date of withdrawal, and any subjects without menstrual bleeding prior to the end of study visit will be censored in this analysis at the date of the last known menses status study visit. Any subjects who doesn't stop menses during the treatment duration (V2 till V8) are excluded this analysis. "Stop menses" is considered as at least one answer "No" for the question "Is the menses recovered since last visit" in CRF page "Status of Menses" at least 2 consecutive menses stop during treatment duration (V2 till V8).

Statistical Analysis Plan

Version: Final 3.1

Ipsen Pharma; Protocol No. D-CN-52014-220

Date of Issue: 13DEC2019

CCI

The number and percentage of subjects with menses recovery and censored subjects and their censor reasons will be summarised. The median time, 25th and 75th quartile times and their 95% CIs will be estimated using the Kaplan-Meier method; Kaplan-Meier curves will be plotted.

7.6.3 Subgroup Analysis

The primary efficacy endpoints and secondary efficacy endpoints (except time to menses recovery) will be analysed by subgroups of randomisation stratification factors:

- Endometriotic surgical history (previous surgery, no previous surgery)
- Severity of endometriosis-associated pelvic pain at baseline (VAS>3 cm, VAS≤3cm).

7.6.4 Exploratory Analysis

The analyses of exploratory efficacy endpoints (see Section 3.3) will be performed on the FAS subjects using as-randomised assignments.

Percentage of subjects castrated 1) $E_2 \leq 184$ pmol/L (50 pg/mL) 2) $E_2 \leq 110$ pmol/L (30 pg/mL) at Week 24:

The number and percentage of subjects castrated (according to each criterion) will be presented by treatment group at Week 24. The difference in percentage between the treatment groups and its 2-sided 95% CI will be presented and calculated using the same method as primary efficacy analysis.

Change in endometriosis-associated pelvic pain (by 10cm VAS) at Weeks 16, 20 and 24 and the end of study visit compared to baseline:

Endometriosis-associated pelvic pain measured by 10 cm VAS and change from baseline, will be summarised by treatment groups and overall at each time point, using summary statistics (n, mean, median, SD and minimum and maximum values) and the 95% CI for the true difference in mean VAS score and VAS change from baseline scores will be presented.

The 95% CI for difference in mean and change from baseline values are calculated using MMRM, same as those used in secondary analyses of VAS.

The mean and change from baseline of VAS at each time point are also analysed by subgroups of baseline VAS (VAS>3 cm, VAS≤3cm).

Serum E2, FSH and LH Concentrations at Week 24:

Serum E2, FSH and LH concentrations and change from baseline will be summarised at Week 24, using descriptive statistics (n, mean, median, SD and minimum and maximum values) and the 95% CI for the difference between treatment groups in mean concentration values and mean change from baseline values will be presented for each parameter.

The 95% CI for the difference in mean and change from baseline values are calculated using MMRM, same as those used in secondary analyses of VAS.

The PK/PD relationship will be explored (PD markers being E2, FSH and LH).

The data for subject individual plasma triptorelin concentration and PD markers in the each treatment groups will be combined to explore the relationships between PK concentrations and PD markers on the PK/PD relationships analysis set. PK/PD modelling will be described in a separate data analysis plan and reported in a standalone report.

7.7 Safety

All safety data will be included in the data listings. Analyses and summary tables will be based on the Safety Set. Safety endpoints will be analysed using descriptive statistics.

7.7.1 Adverse Events

A treatment-emergent adverse event (TEAE) is defined as any AE that occurs or worsens on or after the first dose of IMP, through 112 days (16 weeks) after last injection for triptorelin pamoate PR 3-month groups or through 56 days (8 weeks) after injection for triptorelin acetate PR 1-month group. Non-TEAEs and TEAEs will be separately summarised in tables and all AEs will be presented in the listing with flag of TEAE status.

All adverse events (AEs) recorded on the eCRF will be coded to SOC and PT using the MedDRA dictionary (version number is the newest version used in Covance coding system at the time of analysis). A subject will be counted at most once within a SOC and PT in summary tables.

In the summary table of TEAEs, the numbers and percentages of subjects and events will be tabulated and presented by treatment groups and overall for the following categories:

- Any TEAEs
- TEAEs with maximum intensity (Severe, Moderate, Mild)
- Serious TEAEs
- Drug-related TEAEs
- Drug-related serious TEAEs
- TEAEs leading to drug withdrawal
- TEAEs leading to drug interruption
- Serious TEAEs leading to drug withdrawal
- Serious TEAEs leading to drug interruption
- TEAEs leading to death

The numbers and percentages of subjects and events will be also be separately summarised by SOC and PT (sorted alphabetically) for each treatment group and overall as the above AE categories. The TEAEs with intensity of Severe will be separately summarised by SOC and PT (sorted alphabetically) for each treatment group and overall. The TEAEs and drug-related TEAEs will be also separately summarised by maximum intensity, SOC and PT (sorted alphabetically) for each treatment group and overall.

TEAEs or drug-related TEAEs with PTs observed $\geq 5\%$ or $\geq 10\%$ of subjects in any one of the treatment groups will be separately summarised by SOC and PTs.

In the event of multiple events being reported by the same subject, the maximum intensity (severe, missing, moderate, mild) and the most serious causality (related, not related) will be chosen. If severity is missing for one event and the subject had no intensity of severe in the same category events, “missing” row should be added after severe in the summary tables with maximum intensity.

Statistical Analysis Plan

Version: Final 3.1

Ipsen Pharma; Protocol No. D-CN-52014-220

Date of Issue: 13DEC2019

CCI

The following AEs for each subject will be separately listed, including SOC, PT, and the original (verbatim) term reported by Investigator:

- All AEs
- Serious AEs
- Drug-related AEs
- AEs leading to drug withdrawal
- Deaths

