5.2.3 Procedures during Study Treatment (Visit 2 Postdose to Visit 8)

Subjects receiving triptorelin acetate PR 1-month will receive study drug at each visit during the treatment period up to and including Visit 7 (Week 20, Day 141±3). Subjects receiving triptorelin pamoate PR 3-month will receive study drug at Visit 2 (Day 1) and Visit 5 (Week 12, Day 85±3) only.

The following procedures will be performed on all subjects at Visit 3 (Week 4, Day 29±3) and Visit 4 (Week 8, Day 57±3):

- Efficacy assessments (E₂, LH and FSH concentrations (samples taken predose for subjects receiving triptorelin acetate PR 1-month); VAS)
- Samples taken for sparse PK analysis (samples taken predose for subjects receiving triptorelin acetate PR 1-month)
- Vital signs
- Review of AEs

- New or changed concomitant medications/therapies
- Review of menses status and record date of menses onset (if applicable)
- Injection of IMP (subjects receiving triptorelin acetate PR 1-month only)

The following procedures will be performed at Visit 5 (Week 12, Day 85±3):

- Efficacy assessments (E₂, LH and FSH concentrations (samples taken predose for all subjects); VAS)
- Samples taken for sparse PK analysis (samples taken predose for all subjects)
- Physical examination
- Pelvic examination
- Vital signs
- Laboratory safety tests (blood sampling for biochemistry, haematology and urinalysis)
- 12-lead ECG
- Pelvic type B ultrasound scan (optional based on subject's disease condition, as judged by the investigator)
- Review of AEs
- New or changed concomitant medications, including details of any "add back" therapy
- Review of menses status and record date of menses onset (if applicable)
- Injection of IMP (all subjects)

The following procedures will be performed at Visit 6 (Week 16, Day 113±3) and Visit 7 (Week 20, Day 141±3):

- VAS assessment
- Vital signs
- Review of AEs
- New or changed concomitant medications/therapies, including details of any "add back" therapy
- Review of menses status and record date of menses onset (if applicable)
- Injection of IMP (subjects receiving triptorelin acetate PR 1-month only)

The following procedures will be performed at Visit 8 (Week 24, Day 169±3):

- Efficacy assessments (E₂, LH and FSH concentrations; VAS)
- Physical examination
- Pelvic examination
- Vital signs
- Laboratory safety tests (blood sampling for biochemistry, haematology and urinalysis)
- 12-lead ECG
- Pelvic type B ultrasound scan
- Samples taken for sparse PK analysis

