6.3 Procedures for Monitoring Subject Compliance

The investigator will be responsible for monitoring subject compliance. Subjects can be withdrawn from the study at any time if the investigator or the sponsor determines that the subject is not in compliance with the study protocol.

For this study, all doses of IMP will be administered to the subjects at the study centre by study site staff. Administration of IMP must occur at the study day indicated ± 3 days. Administration compliance will be assessed by comparing the number of doses expected with the number of doses administered. Any missing injection at Visits 2, 3 or 4 (Day 1, Week 4 or Week 8) will be regarded as a major protocol violation.

Where a subject is consistently noncompliant with IMP intake they should be discontinued from IMP/withdrawn from the study. Please refer to Section 4.3 for the criteria for discontinuing the subject from IMP.

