- **Prolongation of hospitalisation** is defined as any extension of an in-patient hospitalisation beyond the stay anticipated/required in relation to the original reason for the initial admission, **as determined by the investigator or treating physician**. For protocol-specified hospitalisation in clinical studies, prolongation is defined as any extension beyond the length of stay described in the protocol. Prolongation in the absence of a precipitating, treatment emergent, clinical AE (i.e. not associated with the development of a new AE or worsening of a pre-existing condition) may meet criteria for "seriousness" but is not an adverse experience and thus is not subject to immediate reporting to the sponsor.
- Preplanned or elective treatments/surgical procedures should be noted in the subject's screening documentation. Hospitalisation for a preplanned or elective treatment/surgical procedure should not be reported as an SAE unless there are complications or sequelae which meet the criteria for seriousness described above.

Any SAE must be reported immediately (within 24 hours) using the fax number specified at the beginning of this protocol, independent of the circumstances or suspected cause, if it occurs or comes to the attention of the investigator at any time during the study period.

Any AE/SAE with a suspected causal relationship to IMP administration occurring at any other time after completion of the study must be promptly reported.

The following information is the minimum that must be provided to the sponsor within 24 hours for each SAE:

- Study number
- Centre number
- Subject number
- AE
- Investigator's name and contact details

The additional information included in the SAE form must be provided to the sponsor or representative as soon as it is available. The investigator should always provide an assessment of causality for each event reported to the sponsor. Upon receipt of the initial report, the sponsor will ask for the investigator's causality assessment if it was not provided with the initial report.

The investigator should report a diagnosis or a syndrome rather than individual signs or symptoms. The investigator should also try to separate a primary AE considered as the foremost untoward medical occurrence from secondary AEs which occurred as complications.

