10.4.8 Safety Evaluation

All safety data will be included in the subject data listings. Analyses and summary tables will be based upon the safety set.

All AEs will be coded according to the Medical Dictionary for Regulatory Activities (MedDRA) version current at the start of the study, and will be classified by MedDRA preferred term and system organ class. AE listings will be presented by subject, system organ class and preferred term.

The incidence of all reported treatment-emergent adverse events (TEAEs) and SAEs will be tabulated by treatment group and overall. In addition, summary tables will be presented by maximum intensity, drug relationship and TEAEs associated with premature withdrawal of study medication.

A TEAE is defined as any AE that occurs from receiving the first dose of study drug to the end of study/early withdrawal visit if:

- it was not present prior to receiving the first dose of study drug, or
- it was present prior to receiving the first dose of study drug but the intensity increased during the active phase of the study.

All TEAEs will be flagged in the AE listings.

Prior and concomitant medication will be coded by using the World Health Organisation (WHO) Drug Dictionary (version December 2016 or above) and will be summarised separately by treatment group and overall with the number and percentage of subjects receiving prior and concomitant medication by drug class and preferred drug name. Prior medications/therapies are all those stopped prior to the first dose of study drug and concomitant medications/therapies are defined as all those ongoing or started at/after the first dose of study drug.

For laboratory data, abnormal values will be flagged in the data listings and a list of clinically significant abnormal values will be presented. Shift tables will be presented of the number and percentage of subjects with low, normal or high values and normal or abnormal physical/pelvic examination findings between baseline and Week 24 time points.

Vital signs data will be presented as shift tables, with the number and percentage of subjects with normal or abnormal findings between baseline and each assessment.

ECG data will also be presented as shift tables, with the number and percentage of subjects with normal or abnormal findings between baseline and Week 12 and Week 24.

Serum E₂, FSH and LH concentrations at Week 40 will be listed only.

Detailed methodology for the analysis of safety data will be presented in the SAP.

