8 CHANGES IN PLANNED ANALYSES

Not applicable.

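### The protocol and the SAP close the treatment-emergent window for new-onset events at different times (final visit, at latest Day 281±3, versus Day 197 for on-schedule dosing), and the SAP declares no change

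*SAP*

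**What the plan says.** Protocol 10.4.8 has one rule for both arms: "A TEAE is defined as any AE that occurs from receiving the first dose of study drug to the end of study/early withdrawal visit". The event must either be absent before the first dose, or be present and become more intense in what the protocol calls the active phase of the study, a term it does not define. The same section adds: "Detailed methodology for the analysis of safety data will be presented in the SAP".

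SAP 7.7.1 ties the window to dosing instead. An event counts if it occurs or worsens from the first dose "through 112 days (16 weeks) after last injection for triptorelin pamoate PR 3-month groups or through 56 days (8 weeks) after injection" in the 1-month arm. Only the 3-month clause says that the count starts at the last injection. The section goes on: "Non-TEAEs and TEAEs will be separately summarised in tables". The tables by intensity, seriousness, drug relationship, frequency and death are specified for TEAEs. The listings of all, serious and drug-related AEs, AEs leading to drug withdrawal, and deaths are not limited to TEAEs.

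SAP 8, where changes from the planned analyses belong, reads "Not applicable". The SAP version history records edits to 7.7.1 but no change to the length of the window.

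**The concern.** One trial has two definitions of its main safety category. Safety is a secondary objective (Protocol 2.2), and the summary tables that readers use are built on TEAEs.

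AE review is planned beyond the SAP cut-off: by telephone at Weeks 32 and 36 if required (Protocol 5.2.4.1) and at the end of study visit (Protocol 5.2.4.4). Take a new, drug-related serious event on Day 210 in a subject followed to Week 40. Under the protocol it is a serious, drug-related TEAE. Under the SAP it is absent from those tables and falls in the Non-TEAE summary, which also holds pre-dose events. Anyone comparing the report with the protocol would find TEAE counts that do not match, with no explanation.

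**Working it through.** **Inputs**
- SAP window: 112 days (3-month) and 56 days (1-month), SAP 7.7.1. For the 1-month arm I read injection as last injection.
- Last scheduled injection, 3-month: Day 85±3 (Protocol 5.2.3).
- Last scheduled injection, 1-month: dosing runs "up to and including Visit 7 (Week 20, Day 141±3" days).
- Dosing window: "Administration of IMP must occur at the study day indicated", give or take 3 days (Protocol 6.3).
- Latest final visit: Week 40, Day 281±3 (Protocol 5.2.4.4).

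**Reproducing the plan's figures.** 16 × 7 = 112 and 8 × 7 = 56, as the SAP states. Target day = 7 × week + 1, so Weeks 12, 20, 28 and 40 are Days 85, 141, 197 and 281.

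**SAP close = last injection day + window**
- 3-month: 85 + 112 = Day 197; range 82 + 112 = 194 to 88 + 112 = 200.
- 1-month: 141 + 56 = Day 197; range 138 + 56 = 194 to 144 + 56 = 200.

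**Protocol close for new-onset events.** The final visit, at the latest Day 281 (278 to 284).

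**Difference for a subject followed to Week 40**
- Nominal: 281 − 197 = 84 days.
- Smallest: 278 − 200 = 78. Largest: 284 − 194 = 90.
- As a share of days in that subject's protocol window: 84/281 = 29.9%.
- Of the four follow-up time points (Days 197, 225, 253 and 281), three fall after the SAP cut-off.

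**Worsening of pre-existing events.** The result depends on what the active phase means. If it is the 24-week treatment period, the protocol window ends near Day 169 and the SAP window is 197 − 169 = 28 days longer. If it runs to a Week 40 visit, the SAP window is 84 days shorter. Both are assumptions; the documents do not settle it.

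**Final visit before the SAP cut-off.** Here the SAP window is nominally longer.
- A 3-month subject who leaves at Week 4 after one injection: SAP close 1 + 112 = Day 113, protocol close Day 29, difference 84 days.
- A 1-month subject who leaves at Week 4 without a second injection: 1 + 56 = Day 57, and 57 − 29 = 28 days.
- A fully dosed subject whose menses return on Day 175 has her final visit by 175 + 15 = Day 190, before Day 197.

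So neither window contains the other. AE review stops at the final visit, however, so these extra days should hold few recorded events.

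**The case against.** The best defence is that the protocol hands detailed safety methods to the SAP, and that the SAP window has a visible logic: one dosing interval plus 28 days in each arm (84 + 28 = 112; 28 + 28 = 56). Late events are still summarised as Non-TEAEs, and late serious, related or fatal ones appear individually in the listings. All of this stands, and it limits the harm. It does not remove the conflict, because the protocol section that delegates the detail also fixes its own TEAE definition, and the SAP does not say that it departs from it.

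Protocol 10.4.8 also plans to tabulate TEAEs and SAEs, which can be read as covering SAEs whether or not they are treatment-emergent. That reading does not help the SAP, whose tables cover serious TEAEs.

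A reader might infer three stronger points that the documents do not support.
- *Unequal windows bias the comparison between arms.* For on-schedule subjects both arms close on Day 197, so no such bias is shown.
- *About 30% of TEAEs drop out.* The 29.9% is a share of days for one subject followed to Week 40, not a share of events. Follow-up otherwise ends within 15 days of menses recovery, apart from the PK/PD subgroup's sampling visits, and the documents do not say how many subjects reach Week 40.
- *The longer SAP window for early leavers is an equal problem.* Protocol 8.1.4 says that a suspected-related event "occurring at any other time after completion of the study must be promptly reported". Protocol 5.2.4.4 defines completion as 24 weeks of dosing plus follow-up, so this duty does not plainly cover early leavers. SAP 7.7.1 works from AEs recorded on the eCRF, and the documents do not say that reports made after the study enter it.

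**Conclusion.** The conflict is real and undeclared. For new-onset events in a subject dosed on schedule and followed to Week 40, the SAP moves up to 84 days (78 to 90) of planned AE follow-up out of the TEAE tables. This rests on reading the 1-month clause as counting from the last injection. For worsening events the size cannot be stated until the active phase is defined. For subjects whose final visit precedes the SAP cut-off the difference runs the other way but should matter little.

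No event is lost from the listings. No effect on a TEAE rate, on the between-arm comparison for on-schedule subjects or on the Week 12 primary endpoint is shown. This is a minor to moderate reporting point: it should be corrected, but it does not threaten the trial's main conclusion.

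**What to change.** - Reconcile the two TEAE definitions, including what the active phase means for worsening events, and state which window is the main one.
- Declare the difference in SAP 8 in place of the present entry.
- Insert the word last before injection for the 1-month arm in SAP 7.7.1.
- Add one supplementary set of overall, serious, drug-related and fatal AE summaries covering all events from first dose to the end of study visit.

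The cost is SAP wording and one extra table set, with no new data. The two sets will give slightly different counts, so the report must label the main one clearly.

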7.7.2 Laboratory Evaluations

The central laboratory test results will be collected at screening (Visit 1), Week 12 (Visit 5) and Week 24 (Visit 8), including the following parameters:

- Haematology: red blood cell (RBC) count, haemoglobin, haematocrit, mean corpuscular volume (MCV), mean corpuscular haemoglobin (MCH), mean corpuscular haemoglobin concentration (MCHC), white blood cell (WBC) count with differential (neutrophils, lymphocytes, monocytes, eosinophils, and basophils) and platelet count;
- Biochemistry: urea, creatinine, total bilirubin, conjugated bilirubin, chloride, bicarbonate, sodium, potassium, calcium, inorganic phosphate, alkaline phosphatase, aspartate aminotransferase, alanine aminotransferase, gamma glutamyl transferase, albumin, total protein, total cholesterol, triglycerides, fasting glucose;
- Urinalysis: pH, protein, ketones, glucose, bilirubin, blood, urobilinogen and specific gravity;

Standard international units will be used for summarising quantitative laboratory parameters. Out of reference range values will be flagged as high (H) or low (L) in the listings.

The quantitative laboratory data will be summarised using standard descriptive statistics on actual values and change from baseline at each scheduled visit and final visit for the Safety subjects.

Shift tables presenting movement in and out of reference range (low, normal, high) from baseline to each scheduled post-baseline visit and final visit will be presented by each treatment group and overall. Shift tables presenting movement of clinical evaluation (normal, abnormal not clinically significant, abnormal clinically significant) from baseline to each scheduled post-baseline visit and final visit will be presented by each treatment group and overall as well.

Subjects who became pregnant during the study will be summarised by treatment groups.

Potentially Clinically Significant Abnormalities (PCSA) for Laboratory Tests

The PCSA criteria of some selected laboratory tests in this study are listed in the below table. The number and percentage of subjects with PCSA for each below parameter will be summarised by treatment group and overall at each scheduled visit, final visit and any post-baseline visit. The number and percentage of subjects with abnormal PCSA values (PCSA-low and PCSA-high) at any post-baseline will be summarised by different baseline values (normal, abnormal) and parameters.

Statistical Analysis Plan

Version: Final 3.1

Date of Issue: 13DEC2019

Ipsen Pharma; Protocol No. D-CN-52014-220

CCI

Table 2 PCSA Criteria for Laboratory Tests

Lab Parameter	PCSA – Low Criteria	PCSA– High Criteria	Unit
HGB	≤ 80		g/L
RBC	< 2.8		Tl/L
HCT	< 0.32 and 0.03 decrease from baseline		%
WBC	≤ 2.0	≥ 29	Gl/L
Neutrophil	< 1	> 13	Gl/L
Lymphocyte	< 0.3	> 11.0	Gl/L
Monocytes		> 2.3	Gl/L
Eosinophil		> 1	Gl/L
Basophils		> 0.8	Gl/L
Platelets	< 50	≥ 700	Gl/L
Total Bili		> 3 x ULN	μmol/L
Dir Bili		> 3 x ULN	μmol/L
Alkaline Phosphatase		≥ 3 x ULN	U/L
ALT(SGPT)		≥ 3 x ULN	U/L
AST(SGOT)		≥ 3 x ULN	U/L
GGT		≥ 3 x ULN	U/L
Urea Nitrogen		> 10	mmol/L
Glucose, Fasting	< 3.9	≥ 7.1	mmol/L
Triglycerides		>1.4 (18-20 years) >1.63 (21-30 years) > 1.99 (31-40 years) >2.42 (41-50 years)	mmol/L mmol/l mmol/l mmol/l
Cholesterol		>5.48 (18-20 years) >5.64 (21-30 years) > 6.21 (31-40 years) ->6.85 (41-50 years)	mmol/L mmol/l mmol/l mmol/l
Creatinine		> 154	μmol/L
Calcium	< 1.75	> 3.12	mmol/L
Phosphorus	< 0.65	>1.8	mmol/L
Total Protein	< 40		g/L
Alb BCG	< 25		g/L
Sodium	< 125	> 147	mmol/L
Potassium	< 3.0	> 6	mmol/L
Chloride	≤ 90	≥ 115	mmol/L

Statistical Analysis Plan

Version: Final 3.1

Date of Issue: 13DEC2019

Ipsen Pharma; Protocol No. D-CN-52014-220

CCI

All laboratory data collected during the study will be presented in subject listing with flags indicating out of reference range (low, high), clinical evaluation (abnormal not clinically significant, abnormal clinically significant). If a subject has at least one lab measurement meeting PCSA criteria, all data of that lab parameter will be presented in a separate listing with flag indicating PCSA-low or PCSA high.

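### The haematocrit abnormality limits in SAP Table 2 are on the fraction scale but the unit is printed as %; applied to data held in %, the flag could never be raised

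*SAP*

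**What the plan says.** Table 2 in SAP 7.7.2 lists the PCSA criteria for selected laboratory tests. The HCT row has a low criterion only, "< 0.32 and 0.03 decrease from baseline", and its Unit column reads %.

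The text of the same section states: "Standard international units will be used for summarising quantitative laboratory parameters".

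The criterion feeds two outputs. The first is a set of tables: "The number and percentage of subjects with PCSA for each below parameter will be summarised by treatment group and overall", at each scheduled visit, the final visit and any post-baseline visit, with a further split by baseline status. The second is a listing: "If a subject has at least one lab measurement meeting PCSA criteria, all data of that lab parameter will be presented in a separate listing".

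No hypothesis test is attached. SAP 7.7 says: "Safety endpoints will be analysed using descriptive statistics". Neither document converts the haematocrit limits, explains the % sign, or states the unit in which the central laboratory delivers haematocrit.

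**The concern.** A limit and its unit have to be on one scale before a program can apply them. Here they differ by a factor of 100. The two parts of the rule are joined by *and*, so if the first part cannot be met, no fall from baseline, however large, can raise the flag.

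What is at stake is the haematocrit row of the PCSA tables and the matching listing. If the data are in % and the limits are used as printed, that row shows zeros by construction. Nothing in the output would reveal that the zeros come from the rule and not from the women in the trial.

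**Working it through.** The plan has no calculated figure to reproduce here. The check is whether the printed limits can be met on each possible data scale.

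**Inputs from SAP Table 2:** HCT limits 0.32 and 0.03, unit %; haemoglobin limit 80 g/L; red-cell count limit 2.8 (taken as 10^12/L).

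**Assumptions, not in the documents:** mean cell volume (MCV) 60 to 110 fL; mean cell haemoglobin concentration (MCHC) 280 to 360 g/L. For steps 1 and 2, the decrease is read as an absolute fall of at least the stated amount.

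**Step 1. Conversion.** 0.32 × 100 = 32%, and 0.03 × 100 = 3 percentage points.

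**Step 2. Apply the rule to illustrative pairs.** The flag is raised if HCT is below the limit and the fall reaches the stated amount.

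| Baseline → later HCT (%) | Data in %, limits 0.32 / 0.03 | Data in L/L, limits 0.32 / 0.03 |
|---|---|---|
| 40 → 38 | no | no |
| 40 → 31 | no | yes |
| 38 → 25 | no | yes |
| 36 → 18 | no | yes |
| 36 → 10 | no | yes |

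For 38 → 25 in %, the first condition is 25 < 0.32, which is false. In L/L it is 0.25 < 0.32, which is true, and the fall is 0.38 − 0.25 = 0.13, which exceeds 0.03. Using 32 and 3 on data in % gives the same answers as the last column.

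**Step 3. Scale check against neighbouring rows.**

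- HCT (%) = red-cell count × MCV / 10. At 2.8 this gives 2.8 × 60 / 10 = 16.8% to 2.8 × 110 / 10 = 30.8%.
- HCT (%) = 100 × haemoglobin / MCHC. At 80 g/L this gives 100 × 80 / 360 = 22.2% to 100 × 80 / 280 = 28.6%.
- Against 0.32%, the ratios run from 16.8 / 0.32 = 52.5 to 30.8 / 0.32 = 96. The literal limit is therefore some 50 to 100 times below the level implied by the plan's own red-cell limits.
- An HCT of 0.32% would mean haemoglobin of 0.0032 × 280 = 0.90 to 0.0032 × 360 = 1.15 g/L, which cannot occur in a trial participant.

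**Step 4. Do the neighbouring criteria cover the gap?** An HCT of 32% corresponds to haemoglobin of 0.32 × 280 = 90 to 0.32 × 360 = 115 g/L, and to a red-cell count of 320 / 110 = 2.9 to 320 / 60 = 5.3. Neither range reaches its own limit (80 and 2.8). Under these assumptions, a woman just below 32% would not be picked up by the other two red-cell criteria.

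**Step 5. The second condition.** The text does not say whether the decrease is absolute or relative, or whether it means at least 0.03. On the fraction scale with an absolute reading, any baseline of 0.32 + 0.03 = 0.35 or more makes the second condition automatic once HCT is below 0.32. With a relative reading the same holds from 0.32 / 0.97 = 0.33. The readings can therefore disagree only for women with a baseline below 0.35. At a baseline of 0.34, for example, the absolute reading needs a value of 0.31 or less, while the relative reading is met by anything below 0.32.

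**The case against.** The strongest reply is that the failure is conditional. SAP 7.7.2 calls for standard international units. If haematocrit arrives and is analysed as a fraction, 0.32 and 0.03 work and the defect is one wrong label. That stands. A reader might infer from the table that no woman can ever be flagged, but the documents do not support this without the condition that the data are held in %.

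Second, the SAP version history records that Table 2 was updated in Final 3.0 after findings from the first dry run. This makes an unnoticed failure less likely. It does not show that the haematocrit row was tested, and the row as it now stands still carries the mismatch.

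Third, haematocrit is seen in other ways: descriptive statistics and change from baseline, shift tables by reference range and by clinical evaluation, flagged listings, and adverse event reporting of clinically significant results (protocol 8.1.2.4 and 8.2). Haemoglobin and red-cell count keep working PCSA limits. That stands too, and it bounds the consequence. A reader might infer that an empty row would be taken as evidence of no effect on haematocrit. The documents do not say how the row would be interpreted, and these other outputs would be read beside it.

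Fourth, it is tempting to say that every other row of Table 2 is clean. The cell-count rows carry unit notation (Tl/L, Gl/L) that the SAP glossary does not define and that may come from the PDF conversion. The point does not need that contrast.

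**Conclusion.** The number and the unit in the haematocrit row contradict each other, and nothing in either document reconciles them. The gap is a factor of 100.

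- If data in % are compared with the printed limits, the flag count is zero in both arms whatever the data. This rests only on a haematocrit below 0.32% being impossible.
- If data are in L/L, the rule operates and the error is confined to the label.

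The documents do not settle which applies; the units sentence favours the second. The limits themselves fit the fraction scale and the label does not, a conclusion that the neighbouring limits support under the assumed MCV and MCHC ranges.

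The consequence is limited to one descriptive safety flag and its listing. No efficacy result or formal test depends on it. It is worth correcting because the failure, if it occurred, would be silent, and because the other red-cell criteria do not fully stand in for this one.

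**What to change.** In the HCT row of SAP Table 2, change the unit from % to L/L (fraction) and leave the printed limits as they are. This also brings the row into line with the units sentence in 7.7.2.

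In the programming specification, state the unit of haematocrit in the central laboratory transfer and convert any values reported in % before the rule is applied.

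Ask the sponsor to confirm whether the 0.03 decrease is absolute and whether it means at least 0.03, and write the answer into the row.

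The cost is one table cell, one clarifying phrase and one unit check. If the PCSA outputs have already been produced, only the haematocrit rows and listing need to be checked, and rerun if they were built on % values. No clinical threshold is altered.
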